- Follow-up assessments will occur approximately 12 months and annually thereafter up to 7 years following date of bariatric surgery with an additional assessments at 6 and 18 months following the date of bariatric surgery.
- Participants at NRI who have completed the 7 year assessment will be recontacted to complete the additional 1 time measures and task. This will take place as close to the 7 year appointment as possible.

1 Introduction

1.1 Background. Obesity has become an alarmingly common problem for Americans, with more than 30.4% of adult Americans now being considered obese with a BMI greater than 30 (Hedley, et al., 2004). There is also growing awareness that most obesity treatments that attempt to change food intake and increase physical activity result in modest weight loss at best (Wadden, et al., 1999). Bariatric surgical procedures, on the other hand, particularly the last generation of procedures including RYGBP and Band procedures, have resulted in pronounced and clinically significant reductions in body weight which are well maintained at long-term follow-up. However, there are many aspects of bariatric surgery procedures that remain largely understudied, including predictors of response, feeding problems post-operatively, psychosocial adjustment, and long-term quality of life. The purpose of this study is to bring together expertise in these areas of interest to better understand the outcome of patients who undergo bariatric surgical procedures.

A. Psychopathology and Outcome of Bariatric Surgery

The literature addressing the relationship between comorbid psychopathology and bariatric surgical outcome, as well as long-term psychosocial adjustment and quality of life, is limited. In addition to the fact that only a finite amount of research has addressed these relationships; most of the literature has addressed these problems in ways which markedly limit the interpretability of what has been published:

1. In the vast majority of the published work, routine clinical interviews have been used rather than structured diagnostic psychiatric interviews. The validity and reliability of psychiatric diagnoses made on the basis of such interviews are quite limited, and such a methodology would be unacceptable in contemporary studies of comorbid psychopathology.

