Hörchner and Tuinebreijer (1999) reported significant improvement on the SF-36 one year post-operative Lap-Band placement. Hörchner, et al. (2001) found evidence of significant improvement on three sub-scales on the SF-36 in a two-year follow-up of patients who had undergone the Lap-band procedure. Using a much larger sample, Dixon, et al. (2001) found significant improvements on the SF-36 subscales in a cohort status post Lap-Band placement. They also found that improvement was greater among those with more disability preoperatively, and that the amount of weight loss was not a good predictor of changes in quality of life. Dymek, et al. (2001) administered the SF-36 pre-surgery, 1 to 3 weeks post-surgery, and at 6 month follow-up to 32 morbidly obese subjects and found marked improvement in health-related quality of life, depression, and self-esteem. Our group reported improvement in health-related quality of life at long-term follow-up using the SF-36 (de Zwaan et al., 2002). While most studies indicate that quality of life improves after bariatric surgery, at least one study reported no change. Schok and colleagues in the Netherlands followed 74 patients for one to three years after Lap-Banding and found no significant differences between preoperative and postoperative SF-36 scores at any of the follow-up periods (Schok, et al., 2000).

Studies that assess quality of life outcomes have also been used to compare different types of surgical procedures. For example, Hell, et al. (2000) compared post-surgical changes in quality of life for patients who had undergone either vertical banded gastroplasty, laparoscopic adjustable gastric banding, or RYGBP, finding that although RYGBP patients experienced more weight loss, patients receiving vertical banded gastroplasty and laparoscopic adjustable gastric banding experienced greater quality of life improvements on the BAROS. In another study, laparoscopic RYGBP patients had comparable weight loss at 1 year to patients who received an open RYGBP, but they experienced a more rapid improvement in the QOL than those receiving open RYGBP (Nguyen, et al., 2001). We believe it is essential to study changes in QOL and to relate such changes to the amount of weight loss and weight regain, changes in psychopathology and changes and problems with eating behavior.

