LABS has designed a prospective, longitudinal cohort study with three components. LABS-1 includes all patients who are at least 18 years of age and who undergo bariatric surgery by LABS certified surgeons during a 4 year period, with the primary goal of evaluating the short-term **safety** of bariatric surgery. Important adverse outcomes (i.e., death, rehospitalization, reintervention) occurring within 30 days of surgery are recorded to assess the relationship between short-term morbidity and mortality rates and various patient, operative, and post-surgical care characteristics. LABS-2 will include a randomly-selected subset of patients from the LABS-1 cohort, with the primary goal of evaluating the longer-term **efficacy** of bariatric surgery. More extensive data collection (i.e. demographic, anthropometric, surgical, clinical, and behavioral) and longer follow-up will allow LABS-2 to identify longer-term safety and efficacy (up to 3 years) outcomes, both risks and benefits, and to determine their associations with patient, surgical, and post-surgical care characteristics. Finally, LABS-3, as described in this protocol, will include selected subsets of patients from the LABS-2 cohort to conduct detailed studies of **mechanisms** involved in weight loss and weight gain, energy expenditure, glucose control, and other aspects of the pathophysiology of obesity and obesity-related complications.

This protocol refers specifically to the LABS-3 component (**mechanisms**) of LABS. Specifically, the psychosocial and eating behavior issues that may be related to bariatric surgery.

2 Objectives and hypotheses

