a. Hypothesis #1. Hypothesis #1 posits that patients undergoing bariatric surgery will experience significant decreases in rates of psychopathology and quality of life. This hypothesis will be evaluated using a linear RRM (Gibbons, et al., 1988; Gibbons, et al., 1993; Bock, 1983) for depression (BDI total score) and quality of life (IWQOL-Lite total, SF-36 mental and physical component). A logistic RRM (Stiratelli, et al., 1984) will be used for psychopathology (current mood disorder, current anxiety disorder, current substance use disorder). All of the basic models will include a random effect for subject, and fixed effects for site, assessment time, and time-by-site interaction. Additional variables may include relevant covariates and missing data patterns. Bonferroni contrasts will be used to compare mean scores (for depression and quality of life) or rates of psychopathology between pre-surgical and subsequent assessment points. Analyses will include data from all participants completing at least one post-surgery assessment.

b. Hypothesis #2. Hypothesis #2 states that untreated psychopathology that persists beyond surgery will be associated with less weight loss and poorer quality of life. The effects of post-surgical psychopathology upon weight loss and quality of life will be evaluated using linear RRM's. The basic models will include a random effect for subject, fixed effects for baseline assessment, assessment time, and time-varying covariates for psychopathology (current mood disorder, current anxiety disorder, current substance use disorder, any Axis I disorder). The main effect for assessment time will be used to evaluate within-person change. The use of time-varying covariates for psychopathology allows for the possibility that a given diagnosis may be present for a given subject at one time point but absent at another. Outcome measures for these analyses for weight loss will be BMI, and for quality of life will include the IWQOL-Lite total and SF-36 mental and physical components.

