c. Hypothesis #3. Hypothesis #3 states that untreated psychopathology at the time of bariatric surgery will be associated with increased short-term complications. A logistic regression analysis will be used to evaluate the influence of psychopathology at the time of surgery on short-term surgical complications. Analyses will evaluate the impact upon both DSM-IV diagnostic psychopathology (e.g., current mood disorder, current anxiety disorder, current substance use disorder, any Axis I disorder, any Axis II disorder) and a continuous measure of depressive symptoms, the BDI, upon short-term post-surgical complications.

d. Hypothesis #4. Hypothesis #4 posits that syndromal or subsyndromal eating disorders prior to surgery will be associated a greater frequency of eating disorder symptoms and less weight loss at long-term follow-up. Data from the EDE-BSV and the NDS dietary recall will be aggregated to determine the frequency of various eating disorder symptoms (binge eating, grazing, vomiting, chewing and spitting) at each assessment point. RRM's will then be used to evaluate the effect of pre-surgical eating disorder syndromes (including binge eating disorder and night eating) on eating disorder frequency (Poisson-based RRM) and BMI (linear RRM). The basic models will include a random effect for subject, and fixed effects for site, assessment time, time-by-site interaction, and pre-surgical eating disorder diagnoses (both syndromal and subsyndromal diagnoses).

Power Analysis and Sample Size

Hypothesis #1. Power analyses below assume an attrition rate of 15% at 12 months, and a 10% attrition rate at 24 month assessments. An enrolled sample size of 250 would provide an estimated sample size of 213 at 12 months and 191 at 24 months.

Power analyses regarding the reduction of psychopathology following surgery is based on the finding of Glinski et al. (2001) that 50% of pre-bariatric surgery candidates meet criteria for at least one current Axis I disorder. Assuming a conservative two-tailed alpha of .01, the proposed sample size would provide a power of .90 to detect a reduction in psychopathology of just over 10% from pre-surgery at 12 months and 12% at 24 months (Hintze, 2001). These reductions for Axis I disorders are consistent with those reported in the literature following bariatric surgery (Herpetz et al. 2004).

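### The Hypothesis #2 model list omits site, Hypothesis #3 names no adjustment, and no model for Hypotheses #2 to #4 includes surgical procedure, so these non-randomised associations are open to confounding of unknown size

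*Protocol*

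**What the plan says.** All four models are described in section 4, under Hypothesis Testing.

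- **Hypothesis #1:** "All of the basic models will include a random effect for subject, and fixed effects for site, assessment time, and time-by-site interaction". A following sentence, under this hypothesis only, allows unspecified further covariates.
- **Hypothesis #2** (BMI, IWQOL-Lite, SF-36): "The basic models will include a random effect for subject, fixed effects for baseline assessment, assessment time, and time-varying covariates for psychopathology". Neither site nor procedure is listed.
- **Hypothesis #3** (short-term complications): "A logistic regression analysis will be used to evaluate the influence of psychopathology at the time of surgery on short-term surgical complications". The only predictors named are diagnoses and the BDI.
- **Hypothesis #4** (eating-symptom frequency and BMI): a random subject effect and "fixed effects for site, assessment time, time-by-site interaction, and pre-surgical eating disorder diagnoses (both syndromal and subsyndromal diagnoses". Site is listed and procedure is not.

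The inclusion criteria (3.2.2) require bariatric surgery by a certified surgeon and do not restrict the procedure. Section 1.1 refers to surgical procedures generally, "particularly the last generation of procedures including RYGBP and Band procedures". Part E of the background reports from a comparative study that "although RYGBP patients experienced more weight loss, patients receiving vertical banded gastroplasty and laparoscopic adjustable gastric banding experienced greater quality of life improvements". The description of LABS-2 at the end of section 1 says: "More extensive data collection (i.e. demographic, anthropometric, surgical, clinical, and behavioral". The Site Comparisons paragraph of section 4 tests sites against each other at baseline, on psychopathology among other measures, but provides no adjustment.

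**The concern.** Hypotheses #2 to #4 compare patients who differ in psychopathology or eating disorder, and nothing in these comparisons is randomised. By the protocol's own account, procedure is related to two of the Hypothesis #2 outcomes, and in opposite directions: more weight loss with bypass, larger quality-of-life gains with banding or banded gastroplasty. If the procedure mix differs between exposed and unexposed patients, the exposure coefficient takes up part of the procedure difference and may be inflated or masked. If the mix is the same, the omitted term only adds residual variance.

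Site raises the same issue. The plan adjusts for it in two hypotheses and not in the other two, without a reason. The baseline site comparisons show that the authors thought sites might differ in psychopathology.

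**Working it through.** **1. Terms side by side.**

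| | Site | Time-by-site | Procedure | Further covariates allowed |
|---|---|---|---|---|
| H1 | yes | yes | no | yes, unspecified |
| H2 | no | no | no | not stated |
| H3 | not named | not applicable | not named | not stated |
| H4 | yes | yes | no | not stated |

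The plan has no figure of its own on this point to reproduce.

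**2. What the existing terms remove.** The baseline term in H2 does not remove a difference between procedures that arises after surgery. Site in H4 removes differences in procedure mix between sites but not within a site.

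**3. Illustration for a between-patient contrast.** From section 4: 213 patients at 12 months (250 × .85 = 212.5), 50% with a pre-surgical Axis I disorder, four visits, correlation .30, two-sided alpha .01. Assumed, because the protocol does not give them: about 30% band, a procedure difference D of 0.5 or 1.0 within-procedure SD, and a gap in band share between patients with and without psychopathology. The true psychopathology effect is set to zero.

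Spurious effect = D × gap. False-positive rates come from 4,000 simulated studies per row:

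| D | Band share, exposed v unexposed | Spurious effect (SD) | Rate without procedure | Rate with procedure |
|---|---|---|---|---|
| 0.5 | 30% v 30% | 0 | .012 | .010 |
| 0.5 | 35% v 25% | .05 | .018 | .010 |
| 0.5 | 40% v 20% | .10 | .059 | .009 |
| 1.0 | 30% v 30% | 0 | .011 | .009 |
| 1.0 | 35% v 25% | .10 | .043 | .010 |
| 1.0 | 40% v 20% | .20 | .209 | .010 |

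Hand check of the last row: the variance of a four-visit mean is (1 + 3 × .30)/4 = .475. The unmodelled procedure adds (.40 × .60 + .20 × .80)/2 = .20, so the SD is √.675 = .822. The standard error is .822 × √(4/213) = .113, the shift is .20/.113 = 1.78, and Φ(1.78 − 2.576) is about .21.

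The planning effects of .64 (H2) and .57 (H4) are not conditional on procedure. For comparison with them, divide by √(1 + .21D²), which is 1.026 at D = 0.5 and 1.10 at D = 1.0. The range .05 to .20 then becomes about .05 to .18.

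**4. Illustration for H3.** Assume complication risks of 20% with bypass and 10% with band, and a bypass share of 75% v 65%. The risks are .75 × .20 + .25 × .10 = .175 and .65 × .20 + .35 × .10 = .165, so the spurious odds ratio is (.175/.825)/(.165/.835) = 1.07. With shares of 80% v 60% it is 1.15. With risks of 30% v 10% the two values are 1.12 and 1.25. The planning contrast of 80% v 47% is an odds ratio of (.80/.20)/(.47/.53) = 4.5.

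**5. Cost in power.** For a four-visit-mean contrast with d = .64 and N = 191, power is .9999 without covariates and .9992 if procedure and site together explain 20% of the variance in exposure. For H4 with 100 subjects and d = .57, before attrition, it is .94. If covariates explained 15% of exposure variance, the effective N would be 85 and power .89.

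**The case against.** **The lists are not closed.** H2 and H4 describe basic models, which leaves room for additions, and a separate analysis plan may add them. H3 gives a method and its exposures and no covariate list. A reader might infer that H3 excludes site; the text is only silent. This objection stands and limits the point. The unequal treatment of site in the written lists for H1, H2 and H4 remains.

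**The confounding link is not shown.** A reader might infer that procedure effects do distort H2 to H4. That needs procedure to be associated with exposure in this cohort, and the protocol shows no such association. The survey of surgeons in part C of the background concerns proceeding, postponing or advising against surgery, not bypass versus band. Table 1 tempts further: band series tend to report less baseline binge eating disorder (1% to 29%) than bypass series (17% to 49%). But those are separate studies with different instruments and countries, so they make a link plausible and do not establish it. Section 1.1 also says that part of the assessment is withheld from the surgical team, which weakens one route from research diagnosis to choice of procedure.

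**Procedure may be a mediator.** In H3 and H4 the exposures precede surgery. If they influence the choice of procedure, the unadjusted association is a legitimate quantity. This stands, and is why both estimates are needed. It has little force for H2, where exposure is measured after surgery.

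**The illustration does not represent H2 exactly.** H2 uses time-varying diagnoses. A constant procedure difference does not bias the within-patient part of that coefficient; only the between-patient part, or trajectories that differ by procedure, are affected. The figures match the between-group set-up of the H2 power calculation, not the H2 model.

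**Conclusion.** The omissions are as described. Site is missing from the H2 list without explanation, H3 names no adjustment, and procedure appears in no H2 to H4 model despite open eligibility and the protocol's own evidence that it matters for weight and quality of life. This is a possibility of confounding and a loss of precision, not a demonstrated bias. Its direction and size cannot be derived from the protocol: the effects of .05 to .20 SD and odds ratios of 1.07 to 1.25 rest wholly on assumed procedure differences and shares, and vanish when shares are equal. For H3 even the illustrative effect is small beside the planning contrast. The change is worth making because the comparisons are observational, LABS-2 already collects surgical data, and H1 and H4 already set the pattern for site.

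**What to change.** - **Site:** add site and time-by-site to the H2 models, and site to the H3 logistic model, or state why they are left out.
- **Procedure:** add procedure (RYGBP, band, other, with sparse categories pooled), taken from LABS-1/LABS-2, to the H2 BMI and quality-of-life models, the H3 model, and both H4 models (symptom frequency and BMI).
- **Procedure-by-time:** include a parsimonious term in the BMI and quality-of-life models where the sample supports it.
- **Reporting:** for H3 and H4, give estimates with and without procedure and say what each one answers.

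No new data collection is needed. The cost is parameters. With nine post-operative visits (6, 12 and 18 months, then years 2 to 7) treated as categories, a three-level procedure term with its full interaction adds 2 + 2 × 8 = 18. That is heavy for the 100-subject subset on which H4 is powered, so the time term there should be simple, for example a slope, or procedure should enter as a main effect only.

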**Longitudinal Assessment of Bariatric Surgery (LABS-3):
Psychosocial Issues and Bariatric Surgery**

Design Synopsis

Hypotheses

1. Patients undergoing bariatric surgery will experience significant decreases in the rates of psychopathology, in particular depressive illness, and significant improvements in quality of life, post-operatively.
2. Untreated psychopathology that persists well beyond the surgery (e.g. to one-year follow-up) or that develops post-operatively will be associated with less weight loss and decreased quality of life.
3. Untreated psychopathology at the time of bariatric surgery, including affective disorders and substance abuse/alcohol abuse will be associated with increased short-term (e.g. 90 day) complications (e.g. problems with plugging, vomiting, and dehydration)
4. Syndromal/subsyndromal eating disorders prior to surgery including binge eating disorder and night eating syndrome will be associated with eating disorder symptoms and less weight loss at long-term follow-up.
5. Greater levels of affect dysregulation, greater deficits in cognitive control and greater deficits in reward processing will be associated with less favorable outcomes (higher affective disorder rates, less favorable net weight change, and increased eating disorder pathology/alcohol use pathology) following surgery.

Type of Study

- Prospective cohort study done at three (3) LABS centers.

Inclusion Criteria

- Male and female patients who are at least 18 years of age and undergo bariatric surgery by a LABS certified surgeon.
- Previous enrollment in LABS-1 and LABS-2.
- BMI at baseline of greater than or equal to 35.

Exclusion Criteria

- Informed consent not obtained
- Type 1 Diabetes Mellitus
- Unlikely to comply with follow-up protocol (ie: geographically inaccessible for study visits)
- Unable to communicate with local study staff

Sample Size

- In order to sample a sufficient number of subjects with significant psychopathology at baseline, the sample size for the assessment of psychopathology is 250. The assessment of eating behavior will be done on a subset of 100 subjects.

Duration of Follow-up

- Up to 7 years following bariatric surgery

Outcomes

- Changes in medical and psychosocial measures

Data Collection Schedule

- The LABS-3 Psychosocial baseline data will be collected within 30 days prior to bariatric surgery.

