3.4.1 Clinical Forms and Interview Schedule

Measure/Test	Form Details	Baseline/ Presurgery	6 month follow up	12 month follow up	18 month follow up	annual follow up
PSYCHOPATHOLOGY N= 250						
INTERVIEW						
SCID/IP	Structured Clinical Interview for DSM-IV	X				X
EDE- BSV	Eating Disorders Examination- Bariatric Surgery Version	X		X		X
M-FED-BSV	MFED- Bariatric Surgery Version	X	X	X	X	
SELF-REPORT						
BDI*	Beck Depression Inventory	X	X	X		X
SF-36*	Short Form-36	X	X	X		X
IWQOL- Lite	Impact of Weight on Quality of Life- Lite	X*	X	X*		X*
PETS	Psychiatric and Emotional Test Survey	* X	X	* X	X	* X
MED	Medication Form	* X	* X	* X	X	* X
CTQ	Childhood Trauma Questionnaire					X (one time)
EATING BEHAVIOR N= 100						
NDS	48 Hour Dietary Recall- Nutritional Data System	X	X	X		X

* Gathered as a part of LABS-2

INTERVIEW SCHEDULE WITH NEW MEASURES AND TASKS AT YEAR 7:

LABS Baseline and F/U Funding for Part of Cohort						RO1 Funding				
	Pre-surg	6 mo	1 yr	18 mo	2 yrs	3 yrs	4 yrs	5 yrs	6 yrs	7 yrs
INTERVIEW										
SCID/IP	X				X	X	X	X	X	X
EDE-BSV	X		X		X	X	X	X	X	X
M-FED-BSV		X	X	X	X	X	X	X	X	X
72-hour dietary recall (NDS-R)	X	X	X		X	X	X	X	X	X
SELF-REPORT										
Administered as a part of LABS 2*	X	X	X	X	X	X	X	X	X	X
The following have been added as a new, separate final visit.										
DERS										X
AIM										X
UPPS-P										X
ATQ-ECS										X
SPSRQ										X
Go/No-Go Task										X
Delay Discounting Task										X

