3.4.2 Interview Description

- Structured Clinical Interview for DSM-IV, Patients Edition (SCID-IP; First, et al., 2001). The SCID-P is a widely used semi-structured interview that will be administered to assess comorbid Axis I disorders. Further, an impulse control module will be administered to assess impulsive/compulsive disorders for participants at their 72 month visit and beyond. A review of reliability studies for the SCID found kappa coefficients (measures of inter-rater reliability) ranging from .03 to 1.00, although the majority of the studies found kappas in the range of .7 to .8; test-retest coefficients ranged from .37 to .89.
- M-FED Bariatric Surgery Version (M-FED-BSV). Data will be obtained on other treatment received using the M-FED, an instrument designed for this purpose that has been used in several multi-center BN treatment and longitudinal studies (See for example, Mitchell, et al., 2002; Crow, et al., 2002). A modified version is available for bariatric surgery patients (M-FED-BSV).
- Eating Disorder Examination (EDE-BSV; Fairburn & Cooper, 2006). The diagnostic version of the EDE will be used as the primary measure of eating behavior and pathology. The EDE is an investigator-administered interview used to assess current eating disorder symptoms. The EDE contains four subscales (Restraint, Eating Concern, Shape Concern, and Weight Concern) associated with core psychopathology of eating disorders, as well as frequency measure of binge eating and compensatory behavior. The

validity and reliability of the EDE have been well documented (Fairburn & Cooper, 1993). We have modified a version of the EDE for use with bariatric surgery patient and this form will be used (EDE-Bariatric Surgery Version, EDE-BSV). The modified version of the EDE quantifies eating behavior, experiences of plugging and dumping syndrome, binge eating, grazing, compensatory behaviors, such as vomiting, and chewing and spitting food. This version includes assessment of night eating and excessive fluid intake. The modified version of the EDE has been used in gathering data on eating behaviors in RYGBP patients in prior studies.

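### Hypotheses 2 and 3 are about untreated psychopathology, but their models and power analyses use any current or pre-surgical disorder, with no treatment term

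*Protocol*

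**What the plan says.** The synopsis defines the exposure for Hypothesis 2 as "Untreated psychopathology that persists well beyond the surgery (e.g. to one-year follow-up) or that develops post-operatively" and for Hypothesis 3 as "Untreated psychopathology at the time of bariatric surgery, including affective disorders and substance abuse/alcohol abuse". Section 4 (Hypothesis Testing) restates both with the same qualifier: "untreated psychopathology that persists beyond surgery will be associated with less weight loss and poorer quality of life" and "untreated psychopathology at the time of bariatric surgery will be associated with increased short-term complications".

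The models in those same paragraphs are specified differently. Hypothesis 2 uses linear random regression with "time-varying covariates for psychopathology (current mood disorder, current anxiety disorder, current substance use disorder, any Axis I disorder". Hypothesis 3 uses logistic regression on diagnoses given as examples, ending in "current substance use disorder, any Axis I disorder, any Axis II disorder", and on the BDI as a continuous measure.

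The power section for Hypothesis 2 compares patients with and without pre-surgical psychopathology (d = .64, 50% with an Axis I disorder, two-sided alpha .01, power about .95). For Hypothesis 3 it compares patients with and without a pre-surgical Axis I disorder (80% against 47% with complications, power .98).

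On treatment, Section 3.4.2 says "Data will be obtained on other treatment received using the M-FED". Section 3.4.1 schedules this interview ("MFED- Bariatric Surgery Version") in two tables that do not agree. Section 3.4.3 describes a Medication Form covering medication and supplement use.

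**The concern.** Whether a patient has a current disorder and whether that disorder is untreated are different exposures. A model with only a diagnosis indicator estimates the average association over treated and untreated cases, in whatever mix the cohort happens to have. If treatment reduces the harm, that average understates the association for untreated illness. If treatment goes mainly to the more severe cases, it may overstate it. In either case, a result reported under the hypothesis as worded would claim something about untreated illness that the analysis did not examine.

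This is not a detail that can be assumed to sit in a statistical analysis plan. The protocol itself names the Hypothesis 2 covariates and lists the Hypothesis 3 diagnoses, and neither matches the hypothesis stated in the same paragraph. The sentence allowing further covariates appears only under Hypothesis 1.

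The schedule conflict matters because the M-FED is the instrument named for treatment received, and each table omits it at a visit that one of the two hypotheses depends on.

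**Working it through.** **1. Exposure, side by side.**

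| | Hypothesis as stated | Model as specified | Power groups |
|---|---|---|---|
| H2 | untreated, persisting or new after surgery | current diagnoses, time-varying | any pre-surgical Axis I disorder, yes/no |
| H3 | untreated at surgery | diagnoses at surgery; BDI | any pre-surgical Axis I disorder, yes/no |

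The last two columns contain no treatment term, no restriction to untreated cases and no definition of untreated.

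**2. The stated power reproduces approximately, for any disorder.**

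H2. A single comparison at 24 months, with N = 191 (the protocol's figure) in two equal groups, gives .64 × √(95.5/2) = 4.42. Then 4.42 − 2.576 = 1.85, which is power .968. A linear time contrast over four visits (correlation .30, difference rising from 0 to .64, interim retention assumed between the stated attrition points) gives .939. These bracket the stated .95. The protocol does not specify the time contrast, and a constant difference averaged over four visits would give more than .999.

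H3. With 125 per group, 80% against 47%, alpha .01:
- average rate .635
- standard error under the null: √(2 × .635 × .365/125) = .0609
- standard error under the alternative: √((.80 × .20 + .47 × .53)/125) = .0572
- z = (.33 − 2.576 × .0609)/.0572 = 3.03, power .999. A 94:156 split gives .998, against the stated .98.

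Both figures therefore describe patients with any disorder, treated or not. No stated figure describes the untreated contrast.

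**3. M-FED and SCID schedules (Section 3.4.1).**

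| | Clinical forms table | Year-7 interview schedule |
|---|---|---|
| M-FED | baseline, 6, 12, 18 months; annual blank | pre-surgery blank; 6 months to 7 years |
| SCID | baseline and annual | pre-surgery and years 2 to 7 |

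Under the clinical forms table, no post-surgical visit has both a SCID diagnosis and the M-FED (a problem for H2). Under the year-7 schedule, the pre-surgical visit has the SCID without the M-FED (a problem for H3). The protocol does not say which table governs.

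**4. Axis II.** Section 3.4.2 describes the SCID-IP as assessing Axis I disorders. Neither table contains an instrument identified as Axis II.

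**5. Hypothetical illustration for H2.** The protocol gives no treated share and no effect by treatment, so everything here is assumed. Power .95 at two-sided alpha .01 implies a noncentrality of 2.576 + 1.645 = 4.22. Suppose that d = .64 held in untreated cases only and that half of the diagnosed are treated:

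| Effect in treated cases | Pooled d | Noncentrality | Power, pooled test |
|---|---|---|---|
| 0 | .32 | 2.11 | .32 |
| .32 | .48 | 3.17 | .72 |
| .64 | .64 | 4.22 | .95 |
| .96 | .80 | 5.28 | >.99 |

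Untreated against none compares N/4 with N/2 patients. The variance term rises from 4/N to 6/N, the noncentrality is 4.22 × √(4/6) = 3.45, and power is .81. If a quarter are treated and carry no excess risk, the pooled test has noncentrality 4.22 × .75 = 3.17 (power .72), and untreated against none has 4.22 × √(4/4.67) = 3.91 (power .91).

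**The case against.** The strongest counter-arguments concern the size of the problem.

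A reader might infer that power for Hypothesis 2 really falls from .95 to .32. The protocol does not support that. It derives d = .64 from a correlation with pre-surgical BDI score and applies it to patients with and without any pre-surgical psychopathology, so .64 is already a pooled figure. The .32 requires relabelling it as untreated-only, assuming half are treated, and giving treated patients who still meet criteria no excess risk. Patients whose treatment had fully worked would largely have left the current-disorder group, so no excess risk among those remaining is an extreme assumption. The power calculation also concerns pre-surgical status, not the time-varying covariates of the model. This objection stands.

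A reader might also infer that the treatment data are lost. That is not shown. Each disputed M-FED visit is marked in one of the two tables. The clinical forms table also marks the Medication Form at every visit, and the PETS survey may hold relevant items, although its content is not visible here. What remains is that no model uses any of these sources, and that the Medication Form as described does not cover psychotherapy.

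Finally, the H2 models are called basic, the H3 diagnosis list is by way of example, and an operational definition of untreated could sit in an analysis plan. Yet every listed item is a diagnosis or a symptom score, and the power section makes the same choice. The mismatch is in the protocol's own text.

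**Conclusion.** The mismatch holds and does not depend on any assumption: Hypotheses 2 and 3 concern untreated illness, and their specified models and power analyses concern any disorder. Followed as written, the plan does not test either hypothesis as worded, and the .95 and .98 do not apply to the untreated contrast.

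The size and direction of the bias cannot be determined from the protocol. Under the assumptions in step 5, pooled power ranges from .32 to above .99 depending on the risk in treated cases. The low end is a hypothetical worst case and should not be quoted as the expected loss.

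The M-FED tables conflict at the pre-surgical visit and at annual visits from year 2, and need reconciling. The Axis II analysis cannot be run with the instruments described. That point is minor and separate.

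**What to change.** - In Hypotheses 2 and 3, replace the diagnosis indicator with a three-level factor (none, current and treated, current and untreated), built from the SCID, the Medication Form and the M-FED, and define untreated. Test untreated against none. Do this at least for any Axis I disorder and for mood disorder, where cell sizes allow.
- State that the .95 and .98 power figures apply to any disorder and not to the untreated contrast.
- Where treatment data were not collected, reword the hypothesis to current psychopathology. This matches the listed models and costs nothing.
- Reconcile the two M-FED rows in Section 3.4.1 and state what was actually collected. Some participants have already completed year 7 (synopsis), so past visits cannot be recollected by editing a table.
- Delete the Axis II item from Hypothesis 3.

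The cost is analysis wording, one schedule row and some derivation work on forms already in use. The untreated group is smaller than the diagnosed group: of 125 patients with a disorder (50% of 250), about 62 would be untreated if half were treated, and fewer for less common diagnoses. Treatment status will also remain confounded with severity, so untreated against none is still an observational association.
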